2.4 Clinical safety and Rationale for Dose Selection, Regimen, and Treatment Duration

Osimertinib 80 mg PO once-daily dose, approved by the FDA, has an acceptable safety profile for the intended advanced NSCLC population. The standard clinical practice is to continue targeted therapies until disease progression or unacceptable toxicity.

In the AURA3 study:

The overall incidence of all causality AEs was 97.8% for the osimertinib arm and 99.3% for the chemotherapy arm. Regardless of causality, the majority of all adverse events (AEs) reported with osimertinib were mild or moderate in severity. Adverse events of Common Terminology Criteria for Adverse Events (CTCAE) Grade ≥ 3 were reported for a lower proportion of patients in the osimertinib arm than in the chemotherapy arm: 63 (22.6%) vs. 64 (47.1%) patients, with 16 (5.7%) and 46 (33.8%) of CTCAE Grade ≥ 3 considered related treatment by the investigator for osimertinib and chemotherapy respectively. A number of serious adverse events (SAEs) were reported for patients in the osimertinib arm than the chemotherapy arm: 50 [17.9%] vs. 35 [25.7%] patients. SAEs considered to be possibly related to study drug were less common in the osimertinib arm (8 [2.9%] patients) than the chemotherapy arm (17 [12.5%] patients)

During the treatment period or 28-day follow-up period, death was due to disease under investigation plus a fatal AE in 0.7% of patients in each treatment arm; death due to a fatal AE only occurred in 0.7% osimertinib vs. no chemotherapy patients. All other deaths were due to disease under investigation only.

Osimertinib is well tolerated. Adverse events leading to discontinuation (6.8% osimertinib arm vs 10.3% chemotherapy arm), dose reduction (2.9% osimertinib arm vs 12.5% pemetrexed, 28.6% cisplatin, 10.6% carboplatin of the chemotherapy arm), or dose interruption/delay (12.9% osimertinib arm vs 20.6% pemetrexed, 11.9% cisplatin, and 16.0% carboplatin) were low and less common in the osimertinib arm than in the chemotherapy arm.

The most commonly reported AEs (ie, $>15\%$) in the osimertinib arm vs the chemotherapy arm, respectively were: diarrhea (40.5% vs. 11.0%), rash ([grouped terms] 33.7% vs. 5.9%), dry skin (18.6% vs. 4.4%), decreased appetite (17.9% vs. 36.0%), paronychia (16.5% vs. 1.5%), cough (16.5% vs. 14.0%), nausea (16.1% vs. 49.3%), and fatigue (15.8% vs. 27.9%).

In the osimertinib clinical program:

ILD or ILD-like adverse reactions (eg, pneumonitis) were reported in 3.5% and were fatal in 0.6% (5 patients) of the 833 patients who received osimertinib in AURA studies (who received at least one dose of 80 mg in the 2nd-line or later setting). The incidence of ILD was 8.2% in patients of Japanese ethnicity, 1.9% in patients of non-Japanese Asian ethnicity and 2.9% in non-Asian patients. The median time to onset of ILD or ILD-like adverse reactions was 2.7 months.

Osimertinib leads to a predicted drug-related QTc interval prolongation at the 80 mg dose of 14.2 msec with an upper bound (90% CI) of 15.8 msec, but with no evidence that this is associated with an increased risk of cardiac arrhythmias or Torsades de Point (TdP). In safety dataset of 833 patients in AURA studies treated with osimertinib 80 mg, 0.7% (n=6) were found to have a QTc greater than 500 msec, and 2.9% (n=24) had an increase from baseline QTc greater than 60 msec.

Based on the available clinical trial data, a causal relationship between changes in cardiac contractility and osimertinib has not been established.

Osimertinib has not been associated with gastrointestinal perforations or haemorrhagic diarrhoea and no events leading to dehydration or renal failure have been reported. No severe bullous, blistering or exfoliative skin conditions were observed.

AstraZeneca considers there to be a reasonable possibility of a causal relationship between osimertinib, keratitis and related corneal disorders.

Decreases from baseline in median values for platelets, neutrophils and leucocytes were observed early in treatment with osimertinib. Median values appear to stabilize after the initial drop with the majority of patients experiencing a single grade change or no change in CTCAE grade. As would be expected with the small magnitude of these changes, no clinically significant sequelae in the population have been observed.

Evaluation for potential liver toxicity has shown no apparent association of osimertinib with drug induced liver injury. In the Phase II studies approximately 5% of patients reported AEs of elevations in alanine aminotransferase (ALT) or AST and the vast majority of these elevations were Grade 1 or 2 changes.

There is no apparent association of osimertinib with renal toxicity.

Safety findings in the pooled single-arm Phase II studies were generally consistent with those observed in the osimertinib arm of AURA3. The most commonly reported AEs with osimertinib were low-grade gastrointestinal (GI) disturbances (primarily diarrhea) and skin effects (mainly rashes and acnes, paronychia, and dry skin).

An increased incidence in the ILD reporting rate has been reported for the combination of durvalumab and osimertinib in Study D5160C00006 (the TATTON study). This study showed an incidence rate of 29.4% for pneumonitis/ILD-like events, at a data cut-off of 12 July 2016,

compared with an overall frequency of pneumonitis (including both non serious and serious cases) of around 2% for durvalumab monotherapy across all doses and indications and an overall frequency of pneumonitis/ILD of 2.4% for osimertinib monotherapy.

In Phase I Clinical Pharmacology studies in healthy volunteers osimertinib was generally well tolerated without any significant safety concerns. The healthy volunteer dose limit is set to 80 mg as a single oral dose. Further details are provided in the osimertinib IB version 8.

Clinical experience: Osimertinib Adverse Events

Gastrointestinal tract effects

Osimertinib can cause gastrointestinal tract side effects. Osimertinib has not been associated with gastrointestinal perforations or hemorrhagic diarrhea. No events leading to dehydration or renal failure have been reported. Investigators are advised to follow the general toxicity management guidelines regarding dose interruption and reduction as detailed in Section 9.

Dermatological effects

Osimertinib can cause dermatological side effects (diarrhea, rashes, acnes, paronychia and dry skin). No severe bullous, blistering or exfoliative skin conditions have been reported. Investigators are advised to follow the general toxicity management guidelines regarding dose interruption and reduction as detailed in Section 9.

Ocular surface effects

Keratitis and related corneal disorders have been reported with Osimertinib use. Investigators are advised to follow the general toxicity management guidelines regarding dose interruption and reduction as detailed in Section 9.

Cardiovascular effects

Osimertinib leads to a predicted drug-related QTc interval prolongation at the 80 mg dose, but with no evidence that this is associated with an increased risk of cardiac arrhythmias or Torsades de Point (TdP). Based on available clinical trial data, a causal relationship between effects on changes in cardiac contractility and osimertinib has not been established. Investigators are advised to follow the general toxicity management guidelines regarding dose interruption and reduction as detailed in Section 9.

Respiratory effects

ILD or ILD-like adverse reactions (eg, pneumonitis) have been reported in patients who received Osimertinib who received at least one dose of 80mg in the 2nd line or later setting. An

increased incidence in the ILD reporting rate has been reported for the combination of durvalumab and osimertinib study (TATTION). Investigators are advised to follow the general toxicity management guidelines regarding dose interruption and reduction as detailed in Section 9.

Liver effects

In the Phase II studies, approximately 5% of patients reported AEs of elevations in alanine aminotransferase (ALT) or AST. The vast majority of these elevations were Grade 1 or 2 changes.

Hematopoietic effects

Osimertinib is known to have hematopoietic side effects. Decreases from baseline in median values for platelets, neutrophils and leukocytes were observed early in treatment with osimertinib. Median values appear to stabilize after the initial drop with the majority of patients experiencing a single grade change or no change in the CTCAE grade. Investigators are advised to follow the general toxicity management guidelines regarding dose interruption and reduction as detailed in Section 9.

Reproductive organ effects

No reproductive toxicology or teratogenicity studies have been conducted with osimertinib to date, although the male and female reproductive tracts have been assessed as part of the 1-month toxicology studies.

Renal effects

There is no apparent association of osimertinib with renal toxicity.

3.0 STUDY RATIONALE

3.1 Trial Summary

Abbreviated Title	TOP 1703
Trial Phase	II
Clinical Indication	Stage IV NSCLC (TKI naïve with EGFR mutations: exon 18 G719X, exon 20 S7681 or exon 21 L861Q
Trial Type	Therapeutic treatment
Type of control	Open Label
Route of administration	Tablet(s) taken P.O. (by mouth)
Trial Blinding	Unblinded, open-label
Study Treatment Group	Single Arm Single daily dose of Osimertinib 80mg on days 1-28 of each study cycle.
Number of trial subjects	37
Estimated enrollment period	Approximately 3 years; first patient in First Quarter 2018.
Estimated duration of trial	Estimated at 5 years from the first patient in to last subject's final 2 year follow-up
Duration of Participation	Active study treatment until progression or study treatment not tolerated followed for a maximum of 2 years after completion of study therapy.

3.2 Design and Procedure

This is an open label single arm phase 2 trial of osimertinib with the primary end-point of objective response rate (ORR) as assessed by the investigator, and uses Simon's optimal 2-stage design. All patients will receive the FDA approved dose of osimertinib of 80 mg daily.

3.3 Selection of Subjects

Patients with stage 4 non-small cell lung cancer who have undergone testing for EGFR mutations in a CLIA certified lab will be screened for study participation. Patients are required to demonstrate one of the following EGFR mutations: exon 18 G719X, exon 20 S7681 or exon 21 L861Q. Additional details or the eligibility criteria are in section 5.0

3.4 Duration of Study

At a rate of 1 to 2 patients per month, we expect that trial will take approximately 19~37 months to reach its target accrual if it will not be terminated earlier due to lack of efficacy according to the two-stage design. Patients will continue study therapy until disease progression, unacceptable

25

The information contained in this document is regarded as confidential, and may not be disclosed to another party unless such disclosure is required to initiate the study, to conduct study-related activities, or to comply with national, state, or local laws and regulations. Written authorization from the coordinating site and sponsor is required for disclosure otherwise.

toxicity or withdraw of consent. Patients who discontinue therapy for reasons other than disease progression will be followed for disease progression. After discontinuing study therapy patients will be followed for overall survival every 3 months by telephone or review of medical records until death or a maximum of 2 years from discontinuation of study therapy.

4.0 OBJECTIVES AND ENDPOINTS

Table 1

	Objective	Endpoint	Analysis
Primary	Objective response rate	Patients experiencing a confirmed partial or complete response using RECIST 1.1 (appendix 4)	See Section 22
Key Secondary	Progression-free survival	Time from starting study therapy until disease progression using RECIST 1.1 or death (whichever occurs first) (appendix 4)	See Section 22
Key Secondary	Safety	Common Terminology Criteria for Adverse Events (CTCAE) to assess adverse events	See Section 22
Key Secondary	Overall survival	Time from starting study therapy until death	See Section 22
Exploratory secondary	ORR and PFS in the specific mutation subsets of exon 18 G719X, exon 20 S7681, exon 21 L861Q or compound mutations	RECIST 1.1 (appendix 4)	See section 22

5.0 SUBJECT ELIGIBILITY

The following guidelines are to assist physicians in selecting patients from whom protocol therapy is safe and appropriate. Physicians should consider the risks and benefits of any therapy, and therefore only enroll patients for whom this study treatment is appropriate. For entry into the study, the following criteria MUST be met.

5.1 Inclusion Criteria

Patients are eligible to be included in the study only if they meet **all** of the following criteria. For time limits on imaging and blood tests please refer to on-study Tests and Procedures Table.

1. EGFR mutations as performed on a CLIA certified laboratory demonstrating EGFR exon 18 G719X, exon 20 S768I, or exon 21 L861Q. Patients with compound (also referred to as multiple mutations) will be eligible provided the NSCLC demonstrates one of these mutations.
2. Histological or cytological confirmation diagnosis of Stage 4 NSCLC per [AJCC v7](#).
3. Measurable disease by RECIST 1.1 (please refer to appendix 4)
4. The following laboratory values obtained \leq 14 days prior to study initiation.
 - a. Hematology: ANC \geq 1, 500 / ml, platelet count, \geq 100,000 / ml, hemoglobin \geq 9.0 g / dl
 - Hepatic:
 - b. ALT or ALT $<$ 2.5 times ULN if no demonstrable liver metastases or $<$ 5 times ULN in the presence of liver metastases
 - c. Total bilirubin $<$ 1.5 times ULN if no liver metastases or $<$ 3 times ULN in the presence of documented Gilbert's Syndrome (unconjugated hyperbilirubinaemia) or liver metastases
 - Renal: Cockcroft-Gault calculated creatinine clearance of \geq 45 ml/min or creatinine \leq 1.5 x ULN
5. Have normal QT interval on ECG evaluation QT corrected of \leq 450 ms in males or \leq 470 ms in females obtained from 3 electrocardiograms (ECGs), using the screening clinic ECG machine-derived QTc value
6. Cardiac ejection fraction of \geq 45%
7. Eastern Cooperative Oncology Group (ECOG) performance status of 0 or 1
8. Negative pregnancy test done \leq 7 days (or per institutional policy) prior to treatment, for women of childbearing potential only. Female must use highly effective contraceptive measures, and must have a negative pregnancy test or must have evidence of non-child-bearing potential by fulfilling one of the following criteria at screening:
 - a. Post-menopausal defined as aged more than 50 years and amenorrheic for at least 12 months following cessation of all exogenous hormonal treatments.
 - b. Women under 50 years old would be considered postmenopausal if they have been amenorrheic for 12 months or more following cessation of exogenous

- hormonal treatments and with LH and FSH levels in the post-menopausal range for the institution
- c. Documentation of irreversible surgical sterilization by hysterectomy, bilateral oophorectomy or bilateral salpingectomy but not tubal ligation
- 9. Male subjects must be willing to use barrier contraception
- 10. Age \geq 18 years
- 11. Provision of written informed consent prior to any study-specific procedures

5.2 Exclusion Criteria

Patients will be excluded from the study if they meet **any** of the following criteria:

1. Prior therapy with EGFR TKI therapy
2. Greater than 2 lines of prior systemic therapy for metastatic non-small cell lung cancer.
3. Any cytotoxic chemotherapy or other anticancer drugs from previous treatment regimen or clinical study within 14 days of first dose of study drug.
4. Treatment with an investigational drug within 5 half-lives of the compound
5. Other active malignancy \leq 2 years prior to study enrollment. EXCEPTIONS: Non-melanotic skin cancer or carcinoma-in-situ of the cervix. NOTE: If there is a history of prior malignancy, patients must **not** be receiving other specific treatment (i.e. hormonal therapy) for their cancer
6. Prior radiotherapy \leq 14 days
7. Untreated symptomatic brain metastases (treated brain metastases are allowed provided $>$ 14 days have elapsed from completion of radiotherapy and patient is neurologically stable as assessed by treating physician).
8. Malabsorption syndrome, refractory nausea and vomiting, chronic gastrointestinal diseases, inability to swallow the formulated product or previous significant bowel resection that would preclude adequate absorption of osimertinib
9. Detection of concurrent *EGFR* mutation with exon 20 T790M, exon 19 deletion, exon 21 L858R mutation or exon 20 insertion. Patients with compound (also referred to as multiple mutations) will be excluded if the molecular testing includes one of these mutations
10. Active pregnancy or breast-feeding: Pregnant women are excluded from this study because the effects of osimertinib on the development of the fetus are unknown, and there is potential for teratogenic or abortifacient effects. Because there is an unknown but potential risk for adverse events in nursing infants secondary to treatment of the mother with osimertinib, breastfeeding should be discontinued if the mother is treated with these agents.
11. Grade \geq 2 blurred vision, conjunctivitis, corneal ulcer, dry eye, or keratitis
12. Men who intend to father children during the study or within 4 months afterward are excluded
13. Major surgery within 4 weeks of first dose of study drug.

14. Any unresolved toxicities from prior therapy greater than CTCAE grade 1 at the time of starting study treatment, with the exception of alopecia or neuropathy
15. Currently receiving (or unable to stop use prior to receiving the first dose of study treatment) medications or herbal supplements known to be potent inducers of CYP3A4 (at least 3 weeks prior) (Appendix 2).
16. Significant medical history or unstable medical comorbidities, including but not limited to:
 - a. Heart disease including congestive heart failure (NYHA Grade II or greater); unstable angina; prior myocardial infarction (NSTEMI or STEMI) within 6 months prior to study enrollment; hypertension with a systolic blood pressure of >150 mm Hg **or** diastolic blood pressure of >100 mm Hg while on antihypertensive medication
 - b. Any clinically significant abnormalities in rhythm, conduction or morphology of resting ECG e.g. complete left bundle branch block, third degree heart block and second degree heart block.
 - c. Any factors that increase the risk of QTc prolongation or risk of arrhythmic events such as congenital long QT syndrome, family history of long QT syndrome or unexplained sudden death under 40 years of age in first degree relatives or any concomitant medication known to prolong the QT interval
 - d. Past medical history of interstitial lung disease, drug-induced interstitial lung disease, radiation pneumonitis which required steroid treatment, or any evidence of clinically active interstitial lung disease
 - e. Any evidence of severe or uncontrolled systemic diseases, including uncontrolled hypertension and active bleeding diatheses
 - f. Active infection or ongoing antiviral medication for viral infections including hepatitis B, hepatitis C, or human immunodeficiency virus (HIV). Screening for chronic conditions is not required. HIV-positive participants on combination antiretroviral therapy are ineligible because of the potential for pharmacokinetic interactions with osimertinib.
 - g. Ongoing use of warfarin (injectable low-molecular weight heparins are permitted). Patients must be off warfarin for > 7 days prior to enrollment

5.2 Protocol Eligibility Waivers

No waivers of inclusion or exclusion criteria will be granted. All prospective patients must meet all entry criteria prior to enrollment in the study. If there are any questions regarding the interpretation of an eligibility criterion for a potential patient, contact the principal investigator to discuss the potential patient to confirm eligibility.

6.0 INCLUSION of WOMEN and MINORITIES

There are no exclusions based on gender, race or ethnicity in this trial.

30

The information contained in this document is regarded as confidential, and may not be disclosed to another party unless such disclosure is required to initiate the study, to conduct study-related activities, or to comply with national, state, or local laws and regulations. Written authorization from the coordinating site and sponsor is required for disclosure otherwise.

7.0 REGISTRATION PROCEDURE

Patient registration for all patients signing informed consent will be completed through the Duke Cancer Institute (DCI) Clinical Research Unit (CRU) into EPIC and ONCORE systems within 1 business day of obtaining consent. Patients will be enrolled only after all pre-treatment evaluations are completed and all eligibility criteria are met.

7.1 Registration for Outside Sites

All patients signing informed consent at outside sites must be registered with Duke (including screen failures- indicate screen failure status on last page of eligibility checklist). The following documents are to be completed by the investigator and/or designee and faxed to [contact] or scanned/mailed to the Thoracic Oncology Protocol Office ([contact]): All supporting documents should be sent de-identified.

- TOP 1703 Eligibility Checklist with supporting source documents
- Signed Informed Consent

8.0 STUDY PERIODS (Visit Requirements):

The Schedule of Events (Table 4) summarizes the trial procedures to be performed at each visit. Individual trial procedures are described in detail below. It may be necessary to perform these procedures at unscheduled time points if deemed clinically necessary by the investigator.

For the purpose of scheduling evaluations and to allow for patient and investigator schedules, holidays and weather or other emergencies requiring clinical facilities to be closed, a window of 7 days will be applied to all study visits unless otherwise noted.

Furthermore, additional evaluations/testing may be deemed necessary by the Sponsor and or AstraZeneca for reasons related to subject safety.

TABLE 4: Schedule of Events

Assessment	Screening ¹ Days -28 to 0	D1 of every Cycle ^{1,2,13}	End of Study Treatment (EOT) ³	Follow-up ^{2,4,9}
Informed consent	X			
Inclusion/exclusion Criteria	X			
Demography Baseline Characteristics, Smoking Hx	X			
Medical History⁵	X	X	X	
Prior NSCLC therapies	X			
Physical exam & vital signs⁵	X	X	X	
Height	X			
ECOG Performance Status	X	X	X	
CBC with differential⁶	X	X	X	
Serum Chemistries⁷	X	X	X	
Serum pregnancy test⁸	X	X		
CT scan chest/abdomen⁹	X	X ⁹		
Brain MRI⁹	X	X ⁹		
Echocardiogram /MUGA¹²	X			
EKG¹⁰	X			
Tumor Histology	X			
EGFR mutation status	X			
Adverse event assessment	X	X	X	
Study drug and diary¹¹		Provide & Review	X	
Concomitant Meds	X	X	X	
Subsequent Therapy and Survival Status				X

¹Within 28 days prior to Day 1 of study therapy unless otherwise noted. If screening (baseline) hematology and serum chemistries performed within 14 days of D1 of cycle 1, these do not need to be repeated.

² Unless otherwise noted, a window of 7 days will be applied to all study visits.

³This visit should occur 30 days (+/- 3 days) after study therapy stops for whatever reason (adverse event, progression, or at discretion of the investigator). Patients who have an ongoing grade 4 AE or SAE at the time of discontinuation from study treatment will be contacted every 2 weeks until the event is resolved, determined to be irreversible by the investigator, or until the patient begins an alternate form of treatment. If patient is unable to make appointment due to health reasons (e.g. patient admitted to hospice) or the visit would place an undue burden on the patient in the assessment of the treating physician this visit may be omitted.

⁴ Long-term follow up will occur every 3 months from the last administration of protocol-directed therapy for a maximum of 2 years or until death, whichever occurs first. Subsequent therapy and survival status will be documented. If molecular testing performed (e.g. molecular testing of tumor biopsy or circulating tumor DNA) the results of the testing will be recorded if available. NOTE: follow-up may occur via phone or review of medical records, on-site visits are not required.

⁵Complete history at baseline only, thereafter focused history on symptoms/adverse event. Patients will need baseline evaluation for unexplained eye symptoms to exclude corneal ulceration. Any eye symptoms on study should be referred for full ophthalmologic exam. Vital sign assessment should include B/P, pulse temperature and oxygen saturation. Weight will be taken at screening and Day 1 of every cycle.

⁶This includes CBC with differential (auto or manual) and platelet count

⁷Serum chemistries include blood urea nitrogen (BUN), creatinine, bilirubin, ALT (SGPT), AST (SGOT), alkaline phosphatase. Additional laboratory tests can be ordered if clinically indicated or at the discretion of the investigator but are not required by the protocol

⁸Within 7 days of D1 (or institutional policy) of treatment with study therapy in women of childbearing potential

⁹ CT scan chest and abdomen. MRI of the brain should be performed at baseline on all subjects and with every disease assessment in patients with known brain metastases to assess for intracranial disease progression. Patients without brain metastases will undergo repeat brain imaging as clinically indicated, and patients with brain metastases will undergo repeat imaging every 3 cycles starting with cycle 4 (i.e., cycle 4, 7, 10, 13 etc). CT scan are done on day 1 of cycle 3, and then on cycles 5, 7, 9, 11, and 13 (every 2 cycles for the first year of study therapy), then every 3 cycles (i.e. 16, 19, 22) until disease progression. Patients who discontinue therapy for reasons other than disease progression will be followed for disease progression. The imaging schedule is at the discretion of the treating physician, but the recommended interval is every 6 to 12 weeks. Tumor imaging starting with D1 of cycle 5 may take place within 7 days prior to the study visit to accommodate holiday, weekends, and transportation issues.

¹⁰ EKGs to be obtained in triplicate. EKGs consist of 12-lead studies performed within a 5 minute window after at least 10 minutes rest in supine position. Repeat EKGs may be performed at the discretion of the investigator or per institutional standard.

¹¹ On C1D1 provide the patient medication diary for use. D1 of all subsequent cycles patient diary is to be collected from previous cycle, reviewed with the patient, and a new diary provided. Collect at EOT if not returned earlier.

¹² Echocardiogram or MUGA scan to assess LVEF, testing to be repeated if clinically indicated based on assessment of the investigator or per institutional standard.

¹³To be completed prior to dispensing next cycle.

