9.1.1 Dose Modification

Dose delays and modifications will be made as indicated below. The descriptions and grading scales found in the revised NCI Common Terminology Criteria for Adverse Events (CTCAE) version 4.03 will be utilized for dose delays and dose modifications. A copy of the CTCAE version 4.03 can be downloaded from the CTEP website:

http://ctep.cancer.gov/protocolDevelopment/electronic_applications/ctc.htm.

1. If any patient experiences a CTCAE grade 3 or intolerable grade 2 adverse event related to osimertinib, dosing will be interrupted and supportive therapy administered as per institutional standard. Patients will not be permitted to restart osimertinib until toxicities have resolved to CTCAE grade ≤ 1 .
2. If grade 3 or intolerable adverse event does not resolve with 21 days, patient should permanently discontinue study therapy
3. If first grade 3 or intolerable grade 2 adverse event which resolves within 21 days patient may restart at 80 mg dose level or 40 mg dose delay (at the discretion of the treating physician)
4. If second grade 3 or intolerable grade 2 adverse event which resolves within 21 days patient must have dose reduced to 40 mg daily
5. If patient is on 40 mg dose level and experiences a grade 3 or intolerable grade 2 adverse event patient must discontinue study therapy
6. Patients experiencing corneal ulceration (any grade), interstitial lung disease (ILD), and QT_c interval prolongation with signs/symptoms of serious arrhythmia will permanently discontinue the osimertinib.
7. For patients with grade 3 QT_c prolongation dose reduction to 40 mg daily is mandatory

Patients who are unable to remain on study therapy because of toxicity should be considered for treatment, as per institutional standard.

Dose reduction schema for grade 3 or intolerable grade 2 adverse events.

For specific management other than pulmonary, QT_c prolongation, and corneal ulceration or grade 3 ophthalmologic adverse events please refer to table and text

[figure not shown]

TABLE 2: DOSE REDUCTION

Dose level	Osimertinib dose	Schedule
“0”	80 mg	Daily
“-1”	40 mg	Daily

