16.1 Adverse Events

An adverse event (AE) is any untoward medical occurrence in a subject receiving study drug and which does not necessarily have a causal relationship with this study treatment. For this protocol, the definition of AE also includes worsening of any pre-existing medical condition. An AE can therefore be any unfavorable and unintended or worsening sign (including an abnormal laboratory finding), symptom, or disease temporally associated with the use of study drug, whether or not related to use of the study drug. Abnormal laboratory, physical exam or vital sign findings without clinical significance (based on the PI's judgment) should not be recorded as AEs

From the time that the subject signs the informed consent form through the End of Study Treatment visit (as defined in Section 8.3), all AEs must be recorded in the subject medical record and adverse events case report form.

AEs will be assessed according to the CTCAE version 4.03. If CTCAE grading does not exist for an AE, the severity of the AE will be graded as mild (1), moderate (2), severe (3), life-threatening (4), or fatal (5).

Attribution of AEs will be indicated as follows:

- Definite: The AE is clearly related to the study drug
- Probably: The AE is likely related to the study drug
- Possible: The AE may be related to the study drug
- Unlikely: The AE is doubtfully related to the study drug
- Unrelated: The AE is clearly NOT related to the study drug

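### Non-serious toxicities below grade 4 that end osimertinib have, with a few exceptions, no required AE follow-up after a day-30 visit that may itself be skipped

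*Combined protocol and SAP*

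**What the plan says.** Table 4 (Schedule of Events), footnote 3, places the End of Study Treatment visit 30 days (± 3) after therapy stops. It then adds: "Patients who have an ongoing grade 4 AE or SAE at the time of discontinuation from study treatment will be contacted every 2 weeks", with contact continuing "until the event is resolved, determined to be irreversible by the investigator, or until the patient begins an alternate form of treatment". For patients in poor health, or where attending would be an undue burden, the footnote ends: "in the assessment of the treating physician this visit may be omitted".

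Section 9.1.1 lists reasons for permanent discontinuation. Item 2 reads: "If grade 3 or intolerable adverse event does not resolve with 21 days, patient should permanently discontinue study therapy". Item 5 reads: "If patient is on 40 mg dose level and experiences a grade 3 or intolerable grade 2 adverse event patient must discontinue study therapy". Item 6 opens with "Patients experiencing corneal ulceration (any grade), interstitial lung disease (ILD" and also requires permanent discontinuation. Table 3 in Section 9.1.2 adds drug-related pulmonary events of any grade and clinically significant or persistent eye symptoms.

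Section 16.1 sets the recording period from consent "through the End of Study Treatment visit (as defined in Section 8.3), all AEs must be recorded". After that visit, the only row marked in the Follow-up column of Table 4 is "Subsequent Therapy and Survival Status". Sections 8.4 and 13.2 add follow-up for disease progression in patients who stop for another reason.

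**The concern.** The rule that decides whose toxicity is still followed after treatment does not match the rules that decide whose toxicity ends treatment. The mismatch is plainest under item 2 of Section 9.1.1. A patient stopped under that item has, by construction, an event still ongoing at discontinuation. Unless the event is grade 4 or serious, footnote 3 does not ask for further contact.

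Safety is a key secondary objective, and Section 1.2 asks whether the drug has an acceptable safety profile for further investigation. Whether a toxicity that ended treatment later resolved, persisted or worsened bears directly on that question. The permission to omit the last visit adds a second weakness. It applies to patients in poor health, so missing AE data would be related to the patient's condition.

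**Working it through.** The plan states no figure on this point, so the check is mainly a comparison of the stopping rules with the follow-up rule.

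| Reason for permanent stop | Can it be below grade 4 and non-serious? | Ongoing at the stop? | AE follow-up required after the End of Study Treatment visit? |
|---|---|---|---|
| 9.1.1 item 2: grade 3 or intolerable, unresolved after 21 days | Yes | Yes, by construction | No, unless classed as serious |
| 9.1.1 item 5: grade 3 or intolerable grade 2 on 40 mg | Yes | Possibly | No, unless classed as serious |
| 9.1.1 item 6 and Table 3: corneal ulceration, ILD or related pulmonary event | Yes, no grade floor | Possibly | No, unless grade 4 or classed as serious |
| Table 3: significant or persistent eye symptoms | Yes | Possibly | No, unless grade 4 or classed as serious |
| Table 3: grade 4 events | No | Possibly | Yes, footnote 3, if ongoing |

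**Other text that might close the gap**

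- Appendix 3, Section 4.2: potential Hy's Law cases are monitored until values and symptoms return to normal or baseline, or as long as medically indicated. This is a true exception.
- Table 3: grade 3 liver and creatine kinase values are observed until grade 1. This is arguably an exception, although it appears as guidance beside a treatment interruption.
- Section 16.2: a medically significant condition counts as serious in the investigator's opinion. Some events enter footnote 3 by this route.
- Section 16.2.1: follow-up information including outcome is requested for serious events only.
- Sections 8.4 and 13.2 and footnote 4: progression, subsequent therapy, survival and any available molecular results, but no AEs.

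**Scale**

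Inputs: 37 treated patients (Section 22.4.2) and 6.8% stopping osimertinib for an AE in AURA3 (Section 2.4). Applying that rate to this population is an assumption.

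- Expected AE discontinuations: 37 × 0.068 = 2.5.
- Chance of at least one: 1 − (1 − 0.068)^37 = 0.93.
- At stage 1, with 17 patients: 17 × 0.068 = 1.2, and 1 − (1 − 0.068)^17 = 0.70.

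The 6.8% includes serious and grade 4 events, and the documents do not give the share that is neither. The expected number in the gap therefore runs from 0 (none qualify) to about 2.5 (all qualify and are still ongoing).

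**Timing**

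The text does not define when therapy stops. Counted from the discontinuation decision, the visit falls 27 to 33 days later. Counted from the last dose after a 21-day hold, it falls 27 − 21 = 6 to 33 − 21 = 12 days after the decision. In addition, a visit on day 27 closes AE recording under Section 16.1 before the 30-day serious-event window in Section 16.2.1 ends.

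**The case against.** The strongest reply is that following only grade 4 or serious events after treatment is a deliberate and stated threshold. All AEs are recorded to about day 30, so an event that resolves by then has an outcome and any other is recorded as ongoing. No planned analysis uses AE duration or reversibility. Patients who stop for toxicity remain under follow-up for progression. Eye symptoms on study are referred for a full ophthalmologic examination (footnote 5), and unscheduled procedures are allowed (Section 8.0). ILD that forces a permanent stop could readily be classed as serious. Serious-event reporting does not depend on attending the last visit.

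Most of this stands, and it rules out several stronger readings that a reader might infer:

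- **That treatment-ending toxicities go unrecorded or have no outcome.** They are recorded to the End of Study Treatment visit. What is missing is a requirement beyond it.
- **That every ILD or corneal event falls in the gap.** Some would be serious. That depends on investigator opinion, so the gap there is possible, not established.
- **That the last assessment comes about 9 days after the decision to stop.** This needs the clock to start at the last dose. Footnote 4 refers to the last administration when it means that, and Section 9.1 treats interruption separately, so the discontinuation date is the more natural reading of footnote 3.
- **That a specific number of events will be lost.** The documents give no share from which to compute it. Nor can ILD rates be added to the 6.8%, because the two overlap.

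The reply does not remove the mismatch itself. The progression follow-up carries no AE item, and no substitute AE contact is specified when the last visit is omitted.

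**Conclusion.** The point holds as a gap in required data collection. For non-serious events below grade 4 that end treatment, no AE follow-up is required after the End of Study Treatment visit, apart from the liver and creatine kinase exceptions above. That visit may be skipped without replacement.

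The size is small and uncertain: 0 to about 2.5 expected patients of 37, assuming the AURA3 discontinuation rate carries over. The conclusion takes footnote 3 to cover any ongoing serious event. If grade 4 were read as qualifying both terms, the gap would be wider. The consequence is limited to the completeness of the safety description. The response-rate test and the two-stage decision rule do not change. It merits an inexpensive amendment and does not call the design into question.

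**What to change.** 1. In Table 4, footnote 3, extend the existing two-weekly contact to any AE that led to permanent discontinuation and is still ongoing, whatever its grade. Keep the current end points: resolved, judged irreversible, or alternate treatment begun.
2. Where the End of Study Treatment visit is omitted, collect the AE assessment at about day 30 by telephone or record review, the routes footnote 4 already allows for long-term follow-up.
3. In Section 16.1, align the end of AE recording with the 30-day serious-event window in Section 16.2.1.

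These changes affect data collection only, and no dose or stopping rule is altered. The cost is the amended wording and a few telephone or record-review contacts per affected patient. The limitation is that outcomes will rest on what routine care finds, because no tests are added.
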